2. OBJECTIVES

The primary objective of this study is to develop one or more novel AI-based algorithms (the AI-STROKE algorithms) with optimal diagnostic accuracy for identification of LVO stroke in patients with a suspected AIS in the prehospital setting, based on ambulant EEG data.

The secondary objectives are:

- Assessing the diagnostic accuracy of existing EEG algorithms for identification of LVO stroke in patients with a suspected AIS in the prehospital setting;
- Improving the applicability and reliability of the dry electrode EEG cap for use in the prehospital setting;
- Assessing the logistical and technical feasibility of ambulance paramedics performing ambulant EEGs, using an improved dry electrode EEG cap, in the prehospital setting in patients with a suspected AIS.

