3. STUDY DESIGN

AI-STROKE is an investigator-initiated, multicenter, diagnostic test accuracy study.

PART A: ALGORITHM DEVELOPMENT AND VALIDATION IN THE PREHOSPITAL SETTING

This part is carried out by two ambulance services (Ambulance Amsterdam and Ambulance Noord-Holland Noord). These ambulances almost exclusively transport suspected AIS patients to the following hospitals: AMC, VUMC, OLVG West and Noordwest Ziekenhuisgroep, location Alkmaar. The ambulance services and these hospitals are therefore all participating centers in this study. A single EEG will be performed in patients with a suspected AIS as assessed by the ambulance paramedic, or with a radiologically confirmed LVO (in case of transport to an EVT center). The acquired data will be used for development and validation of one or more AI-algorithms for LVO-detection and validation of existing EEG-algorithms.

PART B: ALGORITHM DEVELOPMENT AND VALIDATION IN THE EMERGENCY ROOM

This part is carried out in the emergency room (ER) of AMC. A single EEG will be performed in patients with a suspected AIS as assessed by the ambulance paramedic that presents the patient to the ER, or with a radiologically confirmed LVO and who are transported to the AMC for EVT. We will use the data for training and validation of one or more AI-algorithms for LVO-detection and validation of existing EEG-algorithms.

At the start of the study, EEG data of suspected AIS patients will be limited. In this phase, we will use existing fully anonymized EEG data, obtained as part of standard medical care, and data from the ELECTRA-STROKE study for pretraining of the AI-algorithms (see chapter 10).

In both study parts a single EEG is performed. After informed consent is given, information is collected on patient characteristics, medical history, medication use, physical and neurological examination performed by the treating physician, imaging studies, diagnosis and treatment as well as logistical and technical information, obtained from the patient, the treating physician and the Emergency Medical Service (EMS). There are no follow up visits.

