EEG data quality will be monitored continuously to avoid an excessive drop-out rate due to malfunctioning EEG hardware. Two interim analyses for the AI algorithms will be performed: the first when 50 and the second when 100 LVO stroke patients are included in the study. Results of these analyses will be obtained by performing k-fold cross-validation on the training data, including data from the ER and the ambulance. The diagnoses (i.e. LVO stroke or no LVO stroke) as predicted by the developed algorithms will be compared to the diagnoses given by the adjudication committee. A receiver operating characteristic (ROC) curve will be plotted for each algorithm and the optimal cut-off value (i.e. highest sensitivity at a specificity \geq 80%) for each algorithm will be determined. For these cut off values, the sensitivity, specificity, negative predictive value and positive predictive value will be reported, including 95% confidence intervals. The steering committee may decide to prematurely stop the recruitment in the study if the results of the interim analysis show that an accurate and stable algorithm can be developed with the data collected up till that point.

Eventually, we will evaluate the performance of the developed classification algorithm(s) and several existing algorithms on the validation data set. A receiver operating characteristic (ROC) curve will be plotted for each algorithm and the optimal cut-off value (i.e. highest sensitivity at a specificity \geq 80%) for each algorithm will be determined. For these cut off values, the sensitivity, specificity, NPV and PPV value will be calculated.

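### Any existing EEG algorithm that already has its own cut-off is never tested at it: section 10 calculates sensitivity, specificity, PPV and NPV only at a cut-off derived in this study

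*Combined protocol and SAP*

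**What the plan says.** Section 2 lists as the first secondary objective "Assessing the diagnostic accuracy of existing EEG algorithms for identification of LVO stroke in patients with a suspected AIS in the prehospital setting". Section 3 says, for both Part A and Part B, that the data will serve "validation of existing EEG-algorithms". Section 8.1.2 makes AUC, sensitivity, specificity, PPV and NPV of existing algorithms a secondary end point.

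The last paragraph of section 10 describes the final analysis, which evaluates the newly developed algorithms and "several existing algorithms on the validation data set". It continues: "A receiver operating characteristic (ROC) curve will be plotted for each algorithm and the optimal cut-off value", defined as "i.e. highest sensitivity at a specificity" of at least 80%, is to be determined for each algorithm. Then: "For these cut off values, the sensitivity, specificity, NPV and PPV value will be calculated". New and existing algorithms are treated alike. Nowhere do the documents apply an existing algorithm at a cut-off fixed before this study.

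**The concern.** Sensitivity, specificity, PPV and NPV belong to a score together with a threshold. If the threshold is replaced, the four measures describe a different rule. An existing algorithm with a defined cut-off would therefore be reported at an operating point chosen here, although the stated aim is to validate the algorithm as it exists.

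The measure most affected is specificity. Section 1 says high specificity may matter even more than high sensitivity, because false positives delay regular treatment and overburden EVT centres. Under the planned rule, reported specificity is held near 80% whatever the existing algorithm would have delivered. If its own cut-off performed poorly on these recordings, the four measures could not show it. This is a question of which rule is evaluated. It would remain if the study-derived cut-off were taken from the training set instead of the validation set.

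**Working it through.** **Reading the text.** The evaluation sentence names developed and existing algorithms. The next sentence sets a cut-off for each algorithm, and the last calculates the four measures at those values. No exception is made for existing algorithms.

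**Size of the validation set.** Inputs from section 4.4: 40 to 100 LVO events, 12% incidence, 30% dropout, maximum 1192 patients. Input from section 10: 20% of the data for validation.
- The plan's own figure: 40/0.12 = 333.3, and 333.3/0.70 = 476.2, so 477 (stated: 484, a difference of 1.4%). 100/0.12 = 833.3, rounded up to 834, and 834/0.70 = 1191.4, so 1192 (stated: 1192). The figure is reproduced closely enough.
- Validation set at the maximum: 1192 x 0.70 x 0.20 = 166.9, about 167 patients.
- LVO: 166.9 x 0.12 = 20.0. Non-LVO: about 147. Patients with a known LVO are also eligible, so the LVO share could be higher.

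**Specificity under the rule.** Lowering a cut-off never reduces sensitivity. The best sensitivity with specificity of 80% or more is therefore always reached at the lowest attainable specificity that satisfies the limit. 0.80 x 147 = 117.6, so 118/147 = 80.3% for any continuous score. If several cut-offs share the top sensitivity, the plan does not say which is taken, and the reported value could lie somewhat higher. Either way the figure comes mainly from the rule.

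**Illustration, all inputs assumed.** The documents give no AUC and no cut-off for any existing algorithm. Take an equal-variance binormal score with d' = sqrt(2) x z(AUC). At AUC 0.80, d' = 1.414 x 0.842 = 1.190. At specificity Sp, sensitivity = Phi(d' - z(Sp)). The planned operating point gives Phi(1.190 - 0.842) = 63.6%. PPV and NPV below use 12% prevalence.

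| Actual specificity of a prior cut-off | 60% | 70% | 80% | 90% |
|---|---|---|---|---|
| Sensitivity, AUC 0.80 | 82.6% | 74.7% | 63.6% | 46.4% |
| PPV, AUC 0.80 | 22.0% | 25.4% | 30.3% | 38.7% |
| NPV, AUC 0.80 | 96.2% | 95.3% | 94.2% | 92.5% |
| Sensitivity, AUC 0.70 | 68.7% | 58.6% | 46.0% | 29.5% |

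The plan would report close to the 80% column in every case.

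The same model can be put as a shift of s SD in all scores, with a prior cut-off that gave 80% specificity and 64% sensitivity in its source setting. Specificity becomes Phi(0.842 - s) and sensitivity Phi(1.190 + s - 0.842). For s = +0.5 these are 63.4% and 80.2%; for s = -0.5, 91.0% and 44.0%. The AUC does not change with s.

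**Could the study see such differences?** Approximate 95% half-widths: sensitivity 1.96 x sqrt(0.64 x 0.36/20) = 21 points; specificity 1.96 x sqrt(0.80 x 0.20/147) = 6.5 points. Specificity at a prior cut-off would be estimated usefully, sensitivity only roughly.

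**Separate from optimism.** In 20,000 simulated validation sets of 20 LVO and 147 non-LVO patients at AUC 0.80, the cut-off chosen by the rule had a mean true specificity of 79.8% against 80.3% reported. Average optimism is small, so it is not what drives this point.

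**The case against.** The strongest reply is that the premise is undocumented. No existing algorithm is named and no cut-off is given. A sentence in section 1, incomplete in the text available, appears to say that the investigators knew of no EEG algorithm developed for LVO detection. The measures that are described (band-power ratios, coherence and phase synchronization in section 1; the theta-alpha ratio and weighted phase lag index in section 4.4) appear without cut-offs. For such measures the planned rule sets a first cut-off and nothing is lost. This stands, and it makes the point conditional.

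Second, a reader might infer that the plan offers no valid accuracy figure for existing algorithms. The documents do not support that: AUC is listed first in the end point, needs no cut-off and is unaffected.

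Third, a reader might assume that every existing algorithm faces new equipment and a new setting. Section 1 says the pilot already used a dry electrode cap applied by paramedics, section 7.1 names the same cap model, and the two predictors in section 4.4 come from that pilot. For those, any shift may be small, although section 3 says the hardware is being optimised.

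Fourth, comparing all algorithms at matched specificity is legitimate and openly stated. This also stands: the study-derived result should be kept. It answers a comparative question, however, and does not replace validation of a rule that already has a threshold.

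**Conclusion.** The point holds in conditional form. As written, section 10 would report any existing algorithm with a prior cut-off only as a re-tuned rule, with specificity at about 80% by construction, for four of the five measures in that secondary end point. This does not match the validation described in sections 2, 3 and 8.1.2.

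The size is unknown. It is tempting to read the shift illustration as an error of 17 to 20 percentage points. The documents do not support that, because the AUC, the prior cut-off and the shift are all assumed, and it is not known whether any included algorithm has a cut-off. Nor can it be said that every existing algorithm is affected. The primary objective and the AUC criterion for the final algorithm are untouched. This is an inexpensive clarification of a secondary end point.

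**What to change.** Add to the last paragraph of section 10:
- For each existing algorithm with a previously defined cut-off, sensitivity, specificity, PPV and NPV with 95% confidence intervals are also reported at that unchanged cut-off, as the validation result. The interim paragraph already asks for 95% intervals; the final paragraph does not mention them.
- The result at the study-derived cut-off is kept alongside, labelled as re-tuned, and used for the matched-specificity comparison with the AI-STROKE algorithms.
- Measures without a prior cut-off keep the current rule and are labelled as having a newly set cut-off.

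The existing algorithms and any prior cut-offs should be listed before the validation data are analysed, so that the category of each is settled in advance. Which of the two results should lead is a matter on which statisticians may differ; reporting both avoids the question.

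The cost is a few sentences in section 10 and one extra results line per affected algorithm, with no new data. Existing algorithms may look less favourable at their own cut-offs than after re-tuning.

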10. ALGORITHM DEVELOPMENT AND STATISTICAL ANALYSIS

ALGORITHM DEVELOPMENT

The EEG data obtained in the prehospital setting and in the ER will be divided in a training (80%) and validation (20%) set. Only the training set will be used to train novel AI-algorithms for LVO-detection. First, we will create a logistic regression model based on standard EEG-features, e.g. time domain characteristics, power spectral density in different frequency bands, coherence measures, and entropy measures. This model will be the reference to assess the improvement of the other novel AI-based models. We plan to base the final AI-STORKE algorithm on artificial neural networks, but other EEG classification algorithms (e.g. based on support vector machines and random forests) may be explored as well.³⁴ First, we will create convolution neural networks (CNN's) using the extracted EEG-features. Subsequently, we will evaluate whether the EEG-signals contain more information than these features by creating models that analyze the time series directly. To deal with the different timescales of features in EEG-signals and their dynamic behavior, we aim to study recurrent neural networks (RNN's). Examples of such RNN's include Long Short-Term Memory (LSTM)^{35, 36}, Gated Recurrent Unit (GRU) CNN's, and Deep Belief networks (DBN's)³⁷. The first models will be built using a limited set of EEG data since data collection is part of this study. We will deal with the data sparsity using two approaches: (I) Transfer learning, we will train models for other EEG classification tasks (such as classification of stroke vs. healthy subjects or male vs. female), so that features from the time signals are trained. For this, existing fully anonymized EEG data will be used. The trained models will subsequently be used to fine-tune the classification of suspected AIS patients. (II) Reinforcement learning³⁸, and uncertainty-based learning in particular. We will update the models by feeding the data that are collected during the study. During the EEG data collection, the algorithm will be evolving, and the correct classification ratio will be improving as more data are added. The final algorithm will be considered successful if an AUC of >0.80 is reached in the validation set.

STATISTICAL ANALYSIS

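### Read as written, the final cut-offs are chosen and assessed in the same validation patients, so reported specificity cannot fall below 80%

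*Combined protocol and SAP*

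**What the plan says.** Chapter 10 splits the data: "The EEG data obtained in the prehospital setting and in the ER will be divided in a training (80%) and validation (20%) set". It protects the validation set from model fitting: "Only the training set will be used to train novel AI-algorithms for LVO-detection". That sentence covers the training of new algorithms. It does not mention cut-offs, nor the existing algorithms.

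The statistical part of the chapter has two parallel paragraphs.

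- **Interim analyses.** The data source is given: "Results of these analyses will be obtained by performing k-fold cross-validation on the training data". Cut-offs are derived there, with "negative predictive value and positive predictive value will be reported, including 95% confidence intervals".
- **Final analysis.** "Eventually, we will evaluate the performance of the developed classification algorithm(s) and several existing algorithms on the validation data set". The next sentence plots a ROC curve per algorithm and determines the cut-off by the same rule as at interim (maximise sensitivity subject to at least 80% specificity). The paragraph ends: "For these cut off values, the sensitivity, specificity, NPV and PPV value will be calculated".

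Nothing carries an interim or training-set cut-off forward, and nothing says a cut-off is locked before validation. How ties are broken among cut-offs with equal sensitivity is not stated. The final sentence names no confidence intervals.

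The formal success criterion does not depend on a cut-off: "The final algorithm will be considered successful if an AUC of >0.80 is reached in the validation set". Sensitivity, specificity, PPV and NPV are secondary end points in section 8.1.2, for new and existing algorithms alike.

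**The concern.** The Introduction describes an instrument that will in the end give a yes/no answer, and says specificity may matter even more than sensitivity, because false positives delay ordinary treatment and overload EVT centres. A validation set should therefore show how a cut-off fixed in advance performs in patients who did not help to choose it.

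If the cut-off is picked on the validation ROC curve under the condition that specificity is at least 80%, the reported specificity is an input presented as a result. Even an uninformative score would report at least 80% specificity, with sensitivity of about 0.20. Its AUC near 0.5 would give it away, but the specificity figure would not. At stake is whether the study can say anything about the binary rule on the property that the protocol stresses, and whether readers can see how uncertain that figure is.

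**Working it through.** **1. Inputs and the plan's own figure.** Section 4.4 gives 40–100 LVO events, 12% LVO incidence and 30% dropout.

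- Upper end: 100/0.12 = 833.3, rounded up to 834; 834/0.70 = 1191.4, rounded up to 1192. This is the stated maximum.
- Lower end: 40/0.12 = 333.3, rounded up to 334; 334/0.70 = 477.1, rounded up to 478. The stated figure is 484, about 1.2% higher, which does not matter here.

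**2. Validation and training sizes.** Of 834 evaluable patients, 100 have LVO and 734 do not. The 80/20 split in chapter 10 gives:

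- Validation: 0.2 × 100 = 20 LVO; 0.2 × 734 = 146.8, about 147 non-LVO.
- Training: 80 LVO and 587 non-LVO.

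The LVO share would be higher if many known-LVO transfers (chapter 3) are enrolled.

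**3. The floor.** Specificity of at least 80% in 147 patients requires at least 0.8 × 147 = 117.6, so 118, true negatives. The reported value is never below 118/147 = 0.803, whatever the score distribution.

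**4. Reported against true values.** Assumption: non-LVO scores N(0,1), LVO scores N(d,1), AUC 0.80, so d = √2 × Φ⁻¹(0.80) = 1.19. At cut-off c, true specificity is Φ(c) and true sensitivity is 1 − Φ(c − d). PPV and NPV use the sample prevalence 20/167. There were 20,000 simulated validation sets under each of two tie rules.

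| 20 LVO / 147 non-LVO | Lowest eligible cut-off: reported vs true | Highest cut-off with the same sensitivity: reported vs true |
|---|---|---|
| Specificity | 0.803 vs 0.797 | 0.834 vs 0.829 |
| Sensitivity | 0.637 vs 0.637 | 0.637 vs 0.589 |
| PPV | 0.303 vs 0.302 | 0.345 vs 0.325 |
| NPV | 0.942 vs 0.942 | 0.944 vs 0.937 |
| 95% range of true specificity | 0.73–0.86 | 0.75–0.91 |
| Sets reported below 0.80 | 0% | 0% |
| Sets truly below 0.80 | about 52% | about 24% |

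Across AUCs of 0.50, 0.75, 0.80 and 0.85, mean specificity bias is 0.4–0.6 points and sensitivity optimism is 0 or 4.6–4.8 points, depending on the tie rule.

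**5. Smaller validation set.** Stopping at the first interim look ("the first when 50 and the second when 100 LVO stroke patients are included in the study") would leave 0.2 × 50 = 10 LVO and about 73 non-LVO patients. Counting only prehospital patients would give a similar size if they were half of the set, but the documents give no such split. True specificity then ranges over 0.70–0.88 or 0.74–0.96 under the two tie rules. Sensitivity is overstated by 0 or 9 points.

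**6. What an interval would add.** The Wilson 95% interval for 118/147 is 0.731–0.859, close to the true range under the first tie rule. Wilson intervals cover true specificity in about 95% of simulated sets.

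**7. Cut-off locked on training data.** It is set on 80/587 and applied to an independent 20/147, assuming out-of-fold scores share the final model's distribution.

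- Mean observed equals mean true: sensitivity 0.636 or 0.624, specificity 0.80 or 0.81 under the two tie rules.
- Observed specificity is below 0.80 in about 48% or 39% of sets.
- A cut-off whose true specificity is 0.70, 0.75, 0.80 or 0.85 is observed below 0.80 with probability 0.997, 0.92, 0.48 or 0.05 (binomial, n = 147).

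**The case against.** The plan sets no pass mark for specificity. The 80% is part of the definition of the cut-off, and success is judged on AUC alone. Sensitivity at a fixed specificity is a standard ROC summary, in which specificity is held by design. The bias is small: with the lowest eligible cut-off, sensitivity, PPV and NPV are essentially unbiased. The 5-point optimism needs the opposite tie rule, and the 9-point figure also needs a much smaller validation set. Confidence intervals alone would reveal most of the hidden spread, and the final sentence may simply abbreviate the interim one. No cut-off guides care in this study.

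The gain from locking is also limited. When true specificity is near 0.80, observing less than 0.80 is close to a coin flip. With 147 non-LVO patients, the 95% interval excludes 0.80 in only 13% (exact) to 17% (Wilson) of sets at a true value of 0.771, 30–36% at 0.75 and 80–84% at 0.70. Locking does not make a true value below 0.80 rarer: 51% or 32% of sets under the two tie rules, against 52% or 24% under the plan. Out-of-fold scores may also be shifted from the final model's. If they sit 0.1 SD lower, true specificity is below 0.75 in 14% or 6% of sets, against 8% or 2% under the plan, and the validation interval excludes 0.80 in only 21% or 14%. Larger shifts are caught more often: 48% or 38% at 0.2 SD, 77% or 68% at 0.3 SD.

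All of this stands, and it limits the point to the secondary end points. It does not remove it. A ROC summary at fixed specificity is legitimate as description, but it does not validate a cut-off. A test with limited power still tells the reader more than a figure that cannot fall below its floor.

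**Conclusion.** The concern holds and should be fixed. Chapter 10 does not state the source of the final cut-offs, and its natural reading has them selected and assessed in the same patients. The text does not expressly rule out a training-set cut-off; if one is intended, the plan should say so.

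On that reading, reported specificity of at least 80% is certain and needs no distributional assumption. The main harm is hidden uncertainty: a reported value fixed at 0.803 under the lowest-cut-off rule stands for a true value anywhere from about 0.73 to 0.86, with no interval requested. Average bias is minor at full size. The sizes rest on the enrolment, dropout and incidence in section 4.4, the 80/20 split, and assumed equal-variance binormal scores with AUC 0.80. The AUC end point and its success criterion are untouched.

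**What to change.** In chapter 10, state that:

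1. Each cut-off is set in the training set, with a stated tie rule. New algorithms use out-of-fold cross-validated predictions. Existing algorithms that are not refitted use their scores in training-set patients, or a published cut-off where one exists.
2. Each cut-off is locked before validation labels are opened and applied unchanged to the validation set.
3. Sensitivity, specificity, PPV and NPV in the validation set are reported with 95% confidence intervals, as at interim.
4. AUC is reported on the validation set as planned. Any sensitivity at 80% specificity read from the validation ROC curve is labelled descriptive.

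The cost is a few sentences and no extra data, since the interim analyses already produce cross-validated training predictions. The price is that observed validation specificity may come out below 80%, in roughly 39–49% of sets when the true value is near 80%, so it must be read with its interval. If only one change is accepted, adding the intervals would reveal most of the hidden spread.
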